## 11. STATISTICAL ANALYSIS

This is an exploratory, feasibility study that serves to provide base case statistics for further prospective research. Primarily descriptive statistics will be used. Demographic and baseline characteristics will be summarized using means, standard deviations, medians, and ranges for continuous variables, and proportions for categorical variables. The PET results will be both qualitatively and quantitatively assessed in 15 patients. Categorical data will be assessed using the Fisher's exact test. Continual data (paired and unpaired) will be assessed using non-parametrical tests (i.e. Mann-Whitney U test and Kruskall-Wallis test).

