### 11.1 Primary study parameter(s)

Tracer pharmacokinetics and the optimal time for scanning will be determined from the data obtained by the serial PET scans in first 5 patients. Output parameters are the radiation absorbed dose to major organs, the effective dose equivalent for patients, the recommended maximum injected dose for  $[^{18}\text{F}]$ PD-L1 and the optimal time point for scanning after tracer administration.

PD-L1 expression in melanoma tumor lesions will be quantified by measuring tracer uptake in tumor lesions. Tracer uptake will be corrected for body weight and injected dose and quantitatively assessed as standardised uptake value (SUVmean with associated standard deviation and SUVmax), which is calculated using the formula: [tissue activity concentration (MBq/g)]/[(injected dose (MBq)/body weight (g)]. SUV will be calculated for all predefined ROI's on the PET-CT scan at baseline. On the PET-CT scan at week 6 of treatment, SUV will be determined for all lesions detected at baseline as well as all newly detected tumor lesions.

Tumor uptake of  $[^{18}\text{F}]$ PD-L1 will be correlated with the amount of PD-L1 expression of melanoma cells and PD-1 and PD-L1 expression on tumor infiltrating immune cells in melanoma lesions. PD-L1 and PD1 expression will be measured by immunohistochemistry. Results of immunohistochemical staining will be described as a semi-quantitative score using the percentage of positive cells (continuous variable), intensity and pattern of staining (discrete variable). This semi-quantitative score will then be correlated to SUV of the corresponding lesion on the  $[^{18}\text{F}]$ PD-L1 PET. Correlation will be expressed as a Pearson/Spearman correlation coefficient depending on distribution of data. Results will be displayed in graphs.

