### 11.2 Secondary study parameter(s)

Heterogeneity between tracer uptake of separate tumor lesions will be determined. For this purpose the absolute difference in SUV between the two PET scans will be determined for all separate lesions and will be visualised in a table. Heterogeneity of this absolute difference in SUV will be analysed for

lesions in one patient (intra-patient heterogeneity) and for lesions between patients (inter-patient heterogeneity).

Although the study population is too small to generate statistical relevant information, the ability of PD-L1 expression to predict response to anti-PD1 treatment will be assessed as a secondary parameter. For this purpose the different lesions identified on the first PET-CT scan, will be qualitatively scored as responding (stable disease, partial or complete regression) or non-responding (progressive disease) according to the RECIST 1.1 criteria. The measured response will then be correlated to the absolute increase in SUV between the two PET scans for PD-L1 expression on PET and response will be correlated to the difference in immunohistochemical score for PD-L1 expression in tumor tissue samples.

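### The lesion-level response analysis in section 11.2 takes no account of the patient, so any p-value or interval from the plan's named methods may be too favourable

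*Combined protocol and SAP*

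**What the plan says.** Section 11.2 sets the unit of the response analysis: "the different lesions identified on the first PET-CT scan, will be qualitatively scored as responding" or not, with the split "stable disease, partial or complete regression) or non-responding (progressive disease) according to the RECIST 1.1 criteria". It continues: "The measured response will then be correlated to the absolute increase in SUV between the two PET scans". A parallel sentence covers tissue: "response will be correlated to the difference in immunohistochemical score for PD-L1 expression in tumor tissue samples".

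The number of lesions per patient is not limited. Section 11.2 states that "the absolute difference in SUV between the two PET scans will be determined for all separate lesions", and section 11.1 that at week 6 "SUV will be determined for all lesions detected at baseline as well as all newly detected tumor lesions". New week-6 lesions fall outside the response analysis, which is confined to lesions seen on the first scan. Section 11.2 also describes heterogeneity within and between patients, so several lesions per patient are expected.

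The general methods are in section 11: "Categorical data will be assessed using the Fisher's exact test" and "Continual data (paired and unpaired) will be assessed using non-parametrical tests (i.e. Mann-Whitney U test and Kruskall-Wallis test". Section 11.1 adds a Pearson or Spearman coefficient, for SUV against immunohistochemistry. No section provides a mixed model, generalised estimating equations, a cluster-robust method, a patient-level summary or a one-lesion-per-patient rule for the response analysis.

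**The concern.** Lesions in one patient share the drug exposure and the host. Under the SUV formula in section 11.1 they also share one body weight and one injected dose per scan. Melanoma and lung cancer are pooled, and the response rates quoted in section 2.2 differ by tumour type and PD-L1 status (8% in low-PD-L1 adenocarcinoma, 30–45% in high-PD-L1 lung cancer, 32% for nivolumab in melanoma). It is therefore plausible, though not shown, that both SUV change and response are more alike within a patient than between patients.

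If so, treating lesions as independent overstates the information in at most 15 patients. Section 11 says the results are to inform later prospective research, so overstated precision could carry into its planning. Even without a test, a pooled coefficient mixes the between-patient with the within-patient association and gives most weight to patients with the most lesions.

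**Working it through.** **Nothing to reproduce.** Section 5.4 gives only 5 + 10 = 15 patients, with no significance level, power, effect size, lesion count or intra-patient correlation.

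**Inputs from the documents.** 10 patients (phase two) or 15 (both phases); binary response per lesion; SUV change per lesion; Mann-Whitney as the named test for a continuous variable in two groups.

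**Assumptions.** Two-sided 5% level; 2 to 15 lesions per patient; intra-patient correlation (ICC) from 0 to 0.7, the same for SUV change and for the latent variable behind response; 50% of lesions responding (60% or 70% in some settings); no true association.

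**Simulation.** Each patient has one random effect for SUV change and another, independent one for response. There were 2,000 runs per setting, so the Monte Carlo standard error is about 0.5 percentage points at 5%. False-positive rate of the lesion-level Mann-Whitney test, 15 patients / 10 patients:

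| Lesions per patient | ICC 0.2 | ICC 0.3 | ICC 0.5 | ICC 0.7 |
|---|---|---|---|---|
| 2 | 4.3% / 5.0% | 5.8% / 5.3% | 6.4% / 7.0% | 8.7% / 7.3% |
| 3 | 5.9% / 4.9% | 5.6% / 5.8% | 10.1% / 8.7% | 12.9% / 11.8% |
| 5 | 5.9% / 5.8% | 8.4% / 8.2% | 11.6% / 12.8% | 19.2% / 21.2% |
| 8 | 7.0% / 8.5% | 9.5% / 7.9% | 18.4% / 17.8% | 27.2% / 28.9% |

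- Unequal counts, ICC 0.5: 12–14% with 2–8 lesions and 20–21% with 5–15.
- Unequal counts, ICC 0.7: about 22% with 2–8 lesions, rising to about 35% with 5–15.
- ICC 0 for both variables, or SUV change clustered at 0.5 and response not clustered: 3.5–5.4%. Inflation needs clustering in both.
- One summary per patient (mean or median SUV change against share of lesions responding, Spearman): about 4–8% throughout.

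**Check by formula.** For an association, the variance inflation is approximately 1 + (m − 1) × ρx × ρy, with m lesions per patient. With half the lesions responding, a latent correlation r becomes (2/π) × arcsin(r) on the binary scale.

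- m = 5, r = 0.5: ρy = (2/π) × arcsin(0.5) = 0.333; inflation = 1 + 4 × 0.5 × 0.333 = 1.67; 1.96/√1.67 = 1.52; two-sided tail = 13%. Simulated: 11.6–12.8%.
- m = 8, r = 0.7: ρy = 0.494; inflation = 1 + 7 × 0.7 × 0.494 = 3.42; 1.96/√3.42 = 1.06; tail = 29%. Simulated: 27.2–28.9%.

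**Effective sample size, 15 patients with 5 lesions each (75 lesions).** For the association at r = 0.5: 75/1.67 ≈ 45. For a mean, the design effect is 1 + (m − 1) × ICC:

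- ICC 0.2: 75/1.8 ≈ 42
- ICC 0.3: 75/2.2 ≈ 34
- ICC 0.5: 75/3.0 = 25
- ICC 0.7: 75/3.8 ≈ 20

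All lie between 15 patients and 75 lesions.

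**The case against.** The strongest reply is that the plan commits to no lesion-level test. Section 11.2 only says that response will be correlated with SUV change. The tests in section 11 are general text, the coefficient in section 11.1 is given for another comparison, and section 11 describes the statistics as mainly descriptive. A reader might infer that the SAP prescribes a Mann-Whitney test on pooled lesions at 5%. It does not; that link is an inference. What remains is that every method the plan names assumes independence, so any p-value or interval drawn from it has this fault.

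Second, section 11.2 itself concedes that the population is too small to be statistically informative, and no decision rests on the result. This limits the harm, but pooling lesions would hide the very smallness that the plan admits.

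Third, strong clustering cannot be presumed. The rationale stresses that PD-L1 expression may differ between metastases, and at an ICC of 0.2, or with two lesions per patient, inflation is small. This stands, and it is why the size is given as a range.

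Fourth, the immunohistochemistry comparison is less exposed, because section 9.4.5 guarantees only one biopsied lesion per patient at each scan. This stands too.

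**Conclusion.** The point holds in a limited form. The analysis unit in section 11.2 is the lesion, the patient plays no part in it, and all named methods assume independence. Lesion-level inference will be too favourable if both variables cluster within patients and patients contribute several lesions. The false-positive rate runs from about 5% to about 35% across the assumed settings. The documents do not allow a narrower range.

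Two stronger readings are not supported. One is that the effective sample size is close to the number of patients. The calculations put it between patients and lesions, approaching the patient count only at high correlation. The other is that this undermines a clear primary endpoint. The Summary (section 1) and section 3.2 list the response association under primary objectives, whereas sections 9.2 and 11.2 treat it as secondary. With that conflict, and with an exploratory and mainly descriptive plan, this is a change that should be made rather than a critical defect.

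**What to change.** In section 11.2:

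1. State that the patient is the independent unit for the response analysis.
2. Base any p-value or interval on one of two approaches. The first is a patient-level summary: each patient's median SUV change against that patient's share of responding lesions, by Spearman correlation with a permutation p-value and n equal to the number of patients. The second is a bootstrap that resamples whole patients. Exchanging whole sets of lesion responses between patients is not straightforward when lesion counts differ, so it is not suggested.
3. Report the number of lesions per patient.
4. Show lesion-level data, including contrasts between lesions within a patient, descriptively and without lesion-level p-values.
5. Give the response association the same status (primary or secondary) in sections 1, 3.2, 9.2 and 11.2.

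The cost is wording only, with no added patient, scan or biopsy. Intervals will be wider. The patient-level summary tests only the between-patient association, so the within-patient question stays descriptive, and with 10 to 15 patients a bootstrap interval is itself approximate.

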### 3.2 Phase two

Primary Objective:

- To assess the association of PD-L1 expression as measured by PD-L1 tracer uptake on PET and PD-L1 expression as measured by immunohistochemical (IHC) staining for PD-L1 of corresponding tumor lesions.
- To correlate response to anti-PD1 treatment with differences in tumor PD-L1 and PD1 expression between baseline and after 6 weeks of treatment, as quantified by PET and IHC analysis.

Secondary objectives:

- To characterize between-subject and within-subject variability in accumulation of the [F]PD-L1 tracer in melanoma and NSCLC metastases.

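### Section 11.2 judges response to anti-PD1 treatment only through lesions on the baseline PET-CT, so progression by new lesions alone never enters the response analysis

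*Combined protocol and SAP*

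**What the plan says.** Section 3.2 lists under the phase-two primary objective: "To correlate response to anti-PD1 treatment with differences in tumor PD-L1 and PD1 expression between baseline and after 6 weeks of treatment". The Summary also places radiological response to anti-PD1 treatment within the phase-two primary objective. Sections 9.2 and 11.2 treat the same question as secondary.

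Section 11.2 sets out the analysis. The units scored are "the different lesions identified on the first PET-CT scan". These "will be qualitatively scored as responding (stable disease, partial or complete regression) or non-responding (progressive disease) according to the RECIST 1.1 criteria". Two correlations follow: "The measured response will then be correlated to the absolute increase in SUV between the two PET scans", and "response will be correlated to the difference in immunohistochemical score for PD-L1 expression in tumor tissue samples".

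On the week-6 scan, section 11.1 states that "SUV will be determined for all lesions detected at baseline as well as all newly detected tumor lesions". Section 9.4.3 applies RECIST 1.1 to the response of tumour lesions and does not mention new ones. Section 9.2 refers to the standard-of-care radiological assessment without saying whether the unit is the lesion or the patient.

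**The concern.** The objective concerns response to a treatment, which is an outcome of the patient. The analysis in section 11.2 concerns the fate of individual lesions already visible at baseline. The two can disagree. A patient may have stable or shrinking old lesions and new metastases at week 6. The plan foresees newly detected lesions, since it measures their uptake, yet nothing lets them change a response label or form part of a patient category.

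For such a patient the response dataset holds no sign that treatment failed. Section 11 says the study is meant to supply base statistics for later prospective research. A lesion-level label reported as RECIST response could be carried forward as if it described patient response.

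**Working it through.** **1. Figures in the plan.** There is no power, effect size or response rate for this analysis to reproduce. The only related figure is the sample size in section 5.4: 5 + 10 = 15, which is correct.

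**2. Where a new lesion could enter.**
- Response label (11.2): restricted to lesions on the first PET-CT, so no.
- SUV correlation (11.2): needs a value on both scans. A new lesion has none at baseline, so no.
- IHC correlation (11.2): needs tissue at both times. Section 9.4.5 asks for at least one biopsy per time point, from the same lesion if possible. A new lesion has no baseline sample, so no.
- Section 11.1: SUV measured at week 6, with no further use stated.
- Sections 9.2 and 9.4.3: no rule for new lesions and no patient category.

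**3. The rule applied to single patients (lesion counts assumed).** The patient-level column assumes that RECIST 1.1 classifies the patient and counts a new lesion as progression. The documents do not reproduce the criteria.

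| Baseline lesions at week 6 | New lesions | Labels under 11.2 | Patient level, new lesions counted |
|---|---|---|---|
| 2 stable, 2 partial regression | 2 | 4 responding, 0 non-responding | progression |
| 1 stable, 1 progressive, 2 partial regression | any number | 3 responding, 1 non-responding | progression if new lesions are present |

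The first row is the problem case. The second shows that it does not cover every patient with new lesions.

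**4. How many patients.** Let q be the share of patients who progress by new lesions only. The documents give no value, so q from 5% to 30% is an assumption. The expected number is n × q, and the chance of at least one such patient is 1 − (1 − q)^n.

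| q | Expected, n = 10 | P(at least one), n = 10 | Expected, n = 15 | P(at least one), n = 15 |
|---|---|---|---|---|
| 5% | 0.5 | 0.40 | 0.75 | 0.54 |
| 10% | 1 | 0.65 | 1.5 | 0.79 |
| 20% | 2 | 0.89 | 3 | 0.96 |
| 30% | 3 | 0.97 | 4.5 | 0.995 |

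For the IHC correlation, if each of the 10 phase-two patients supplies one biopsied lesion, one affected patient is 1/10 = 10% of the data points.

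**5. How far lesion and patient scales can differ (all counts assumed).** Take 10 patients with 4 baseline lesions each: 4 patients without progression, 2 progressing by new lesions only, and 4 in whom 2 of the 4 baseline lesions progress.
- Responding lesions: 4×4 + 2×4 + 4×2 = 32 of 40, or 80%.
- Patients free of progression: 4 of 10, or 40%.
- The 2 new-lesion-only patients supply 8 of the 32 responding labels, or 25%.

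Part of the gap between 80% and 40% comes from the change of unit and only part from new lesions. The example shows that the scales are not interchangeable; it is not a forecast.

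**The case against.** The strongest reply is that section 11.2 scores lesions and scores them correctly: a stable lesion is called stable whatever happens elsewhere in the body. Heterogeneity between lesions is part of the study's rationale, and a correlation with change in SUV can only use lesions that have a baseline value. This stands. A reader might infer that lesion-level scoring is itself the mistake. The documents do not support that, and the lesion-level analysis should stay.

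Other parts of the reply also stand, and they rule out stronger readings:
- A reader might infer that every patient with new lesions contributes only responding lesions. That fails whenever a baseline lesion also progresses.
- A reader might infer that the correlation is diluted or reversed. No calculation from the documents gives a direction or a size.
- A reader might infer that pooling stable disease with regression is an error. It is a choice stated in advance. The response rates in section 2.2 are background and do not define this endpoint. Separate tabulation makes the choice visible.
- A reader might equate newly detected lesions with new metastases. Section 9.4.2 lets lesions be identified on PET or CT, so an old lesion could become visible because its uptake rose.

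It can also be said that section 9.2 leaves room for a patient-level assessment in routine care. It may exist, but section 11.2 does not bring it into the analysis. Finally, the study is exploratory, and section 11.2 concedes that the population is too small for statistical conclusions. That limits the weight of the point without removing it: small numbers reduce precision, whereas this rule determines what is being measured.

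**Conclusion.** The point holds as a gap in the analysis plan. As written, section 11.2 cannot show treatment failure that occurs only through new lesions, although sections 3.2 and 11.2 both frame the question as response to anti-PD1 treatment. What is missing is a patient-level response category and a rule for new lesions.

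The number of patients affected cannot be derived from the documents. Under the assumed 5% to 30%, it is 0.5 to 3 of 10 phase-two patients, with a 40% to 97% chance of at least one. The effect on either correlation is unknown in direction and size. The conclusion also rests on the stated assumption that RECIST 1.1 classifies patients and counts new lesions as progression. Because the analysis is descriptive and no decision rule depends on it, this is a change that should be made, not one that undermines the study.

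**What to change.** In section 11.2:

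1. Keep the lesion-level analysis of SUV change for lesions with a baseline value. Call it lesion-level change, not RECIST response.
2. Add a patient-level overall response by RECIST 1.1 for phase two, in which new lesions confirmed on CT or MRI count as progression. Lesions that are merely newly visible on tracer PET do not. State how brain lesions are handled, since the CT in section 9.4.3 covers chest, abdomen and pelvis, and inclusion criterion 4 measures brain lesions by RANO-BM on MRI.
3. Relate this response descriptively to a per-patient summary of change in SUV and in IHC score, and name the summary in advance.
4. Tabulate CR/PR, SD and PD separately.
5. List new lesions with their week-6 SUV.

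Also reconcile section 3.2, where the response objective is primary, with sections 9.2 and 11.2, where it is secondary.

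The cost is wording, an overall response category recorded for each patient, and one or two tables. No extra scan is needed in phase two if sections 9.4.3 and 9.4.4 are followed. Section 9.4.2 allows a low-dose CT instead, so that should be aligned with section 9.4.3. The downside is that the added analysis has only about 10 units and remains descriptive.

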**Primary objectives:**

Phase one: To assess the dynamics and kinetics of  $[^{18}\text{F}]$ PD-L1 in human subjects to establish optimal scan schedule.

Phase two: To validate the  $[^{18}\text{F}]$ PD-L1 PET tracer by association of PD-L1 tumor expression as determined on PET and PD-L1 expression as determined by immunohistochemistry and to assess the association between the radiological response to anti-PD1 treatment and PD-L1 expression as measured by PET scanning and by immunohistochemistry

**Secondary objectives:** To determine between-subject and within-subject variability in  $[^{18}\text{F}]$ PD-L1 uptake in melanoma and non-small cell lung cancer metastases

**Study design:** This is a feasibility study for the use of  $[^{18}\text{F}]$ PD-L1 as a PET tracer that will be conducted in a single center. The study consists of two phases. The aim of phase one is to provide pharmacokinetic information on the tracer and to determine the optimal time point for imaging. In the second phase the main study objective will be assessed.

**Study population:** The study population consists of patients diagnosed with metastatic melanoma or non-small cell lung cancer that are eligible for treatment with nivolumab, a PD-1 blocking monoclonal antibody. Patients must be at least 18 years of age. In total, a maximum of 15 patients will be included.

**Intervention (if applicable):** The main intervention of this study is a  $[^{18}\text{F}]$ PD-L1 PET scan. In both phase one and phase two a scan sequence will be performed both at baseline and 6 weeks after initiation of nivolumab treatment. The PET scans will be combined with either a low dose or diagnostic CT scan of chest, abdomen and pelvis and a MRI of the brain. In phase two, a biopsy of at least one accessible lesion will be performed to analyze PD-L1 expression using immunohistochemical staining after each PET scan.

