### 2.2 PD1/PD-L1 blockade in melanoma and non-small cell lung cancer

Current first line therapy for patients with unresectable melanoma consists of treatment with anti-PD-1 immunoglobulines such as nivolumab (BMS-936558) or pembrolizumab (MK-3475). Both agents have shown an increase in overall survival in phase III studies, with preferable toxicity profiles as compared to other agents, such as the CTLA-4 inhibitor ipilimumab.

Data from the phase 1 trial for pembrolizumab showed a confirmed response rate in 38% of the patients (9). Objective response rate in a phase 2 trial of nivolumab was 32% (10). Nivolumab led to an even more durable response in patients with stage IV melanoma than ipilimumab, with a median overall survival of almost 17 months compared to 10 months with ipilimumab. In addition, the safety profile of nivolumab is better than that of ipilimumab, with fewer grade 3 or 4 adverse events.

Because of their different mode of action and different phase of T cell activation in which they play a role, combining nivolumab and ipilimumab has been explored in a clinical trial. This combination of CTLA-4 and PD1 blockade led to even higher objective response rates of up to 53%. Recently, this combination therapy has been approved in the Netherlands for the treatment in unresectable melanoma patients. However, the increase in response rates comes at the cost of more toxicity than either single agent (11).

Although efficacy data on immune checkpoint inhibitors are very promising, not all patients will benefit from these agents. Also, immune-related adverse events (irAEs), especially in combination therapy, can limit the use of immune modulating drugs. Key issues in the future of immunotherapy are the understanding of drug kinetics and dynamics in vivo, as well as the effects of these agents on the immune system, since these may be of help in the selection of patients that will benefit from checkpoint inhibiting therapy.

The objective response (ORR) rate of anti-PD-1 therapy in NSCLC varies based on histological subtype and PD-L1 expression of the tumor. For squamous cell and planocellular carcinoma with low PD-L1 expression ORR are 17% and 9% respectively (12,13). For low-PD-L1 adenocarcinoma, ORR is 8%. High PD-L1 expressing tumours show ORR rates of 30 to 45% (14, 15, 16).

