### 2.3 Molecular imaging with [18F]PD-L1

PD-L1 tumor surface expression, which is positive in 40-100% in metastatic melanoma, has been studied intensively as a potential biomarker for the selection of patients that qualify for anti-PD-1 therapy, but not without any obstacles. In early clinical trials, PD-L1 expression has been associated with response to PD1/PD-L1 inhibition (19-21). Later trials reported a response to PD1/PD-L1 checkpoint inhibitors in up to 47% of PD-L1-negative melanomas (22). Also, the potentially heterogeneous expression and fast dynamics of PD-L1 expression make clinical implementation

difficult (19). By labeling of a PD-L1 binding precursor with Fluoride-18 ( $^{18}\text{F}$ ), serial [ $^{18}\text{F}$ ]PD-L1-PET scanning can be used to assess whole body distribution, pharmacokinetics (PK) and pharmacodynamics (PD) and to relate findings to treatment effects. This could help in patient selection and possibly serve as an (early) biomarker for response to PD1/PD-L1 checkpoint inhibitors in the future.

In NSCLC PD-L1 expression is associated with response to therapy, as illustrated above. Therefore, identification of tumors with high PD-L1 expression in this patient category can be of high clinical value.

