#### 9.4.3 CT scan

During phase two, each PET scan will be accompanied by a diagnostic CT scan. The CT scans performed at baseline of treatment with anti-PD1 treatment are part of care as usual. If a diagnostic CT scan has been performed shortly before to inclusion ( $\leq 2$  weeks) this will not be repeated. CT imaging consists of examination of chest, abdomen and pelvis. Response to treatment of tumor lesions will be evaluated according to the RECIST 1.1 criteria.

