### 12.4 Benefits and risks assessment, group relatedness

Molecular imaging with a PET scan is an upcoming technique for obtaining non-invasive whole body information about specific molecular targets. In this imaging study we want to visualize PD-L1 expression in tumor lesions of patients with metastatic melanoma. This tumoral PD-L1 expression could serve as a predictor of response to anti-PD1 treatment. Results of this study could provide valuable information about the whole body distribution of PD-L1 in tumor lesions and heterogeneity in this distribution. In addition, this study will explore how intratumoral PD-L1 and PD1 expression is influenced by anti-PD1 treatment.

Patients will not benefit from participation in this study directly, but their participation helps to develop a new imaging technique which could provide more insights in PD-L1 expression in tumor lesions and predictive value of this PD-L1 expression.

Patients will be treated with anti-PD1 as part of their regular treatment or in the context of a clinical trial. So, this treatment will not cause any additional risk or burden to the patient in this imaging study. Patients will also get regular follow-up to assess disease control.

The tracer was well tolerated in pre-clinical toxicology studies performed in cynomolgus monkeys. For detailed information, we refer to the IB, version 1, 14 Dec 2015.

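### Section 11.2 sets out to test whether PD-L1 expression predicts response, but plans only change-versus-response analyses and never relates baseline SUV or baseline IHC to response

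*Combined protocol and SAP*

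**What the plan says.** Section 11.2 states that "the ability of PD-L1 expression to predict response to anti-PD1 treatment will be assessed as a secondary parameter". For that purpose it scores each lesion seen on the first PET-CT as responding (stable disease, partial or complete regression) or non-responding (progression) under RECIST 1.1. It then names two analyses. For PET, "The measured response will then be correlated to the absolute increase in SUV between the two PET scans". For tissue, response is set against the difference in PD-L1 IHC score. Sections 3.2 and 9.2 frame the response question the same way, as baseline-to-week-6 differences against response.

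Other parts of the document are not limited to change:

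- The Summary's phase-two primary objective is "to assess the association between the radiological response to anti-PD1 treatment and PD-L1 expression as measured by PET scanning and by immunohistochemistry", with no time point.
- Section 12.4 says "This tumoral PD-L1 expression could serve as a predictor of response to anti-PD1 treatment".
- Section 2.3 says of serial scanning: "This could help in patient selection and possibly serve as an (early) biomarker for response to PD1/PD-L1 checkpoint inhibitors in the future".

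The baseline values are collected. Section 11.1 computes SUV for all predefined regions on the baseline scan, and section 9.4.5 provides a phase-two biopsy after each PET scan. The only named use of SUV and IHC levels, in 11.1, is to correlate them with each other.

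**The concern.** A predictor used to select patients must be known before treatment starts. Both analyses in 11.2 use a week-6 value, so they describe an on-treatment association. Followed as written, the study would hold baseline uptake and response for the same lesions with no planned display of one against the other.

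The documents leave the baseline question open. Section 2.2 gives NSCLC response rates by expression level: 8% to 17% with low PD-L1, while "High PD-L1 expressing tumours show ORR rates of 30 to 45" percent. Section 2.3 reports response in up to 47% of PD-L1-negative melanomas.

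Two features make the change analyses weaker still as evidence of prediction:

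- **Timing.** Section 9.4.3 says "During phase two, each PET scan will be accompanied by a diagnostic CT scan" and "Response to treatment of tumor lesions will be evaluated according to the RECIST 1.1 criteria". If response is read on the CT that accompanies the week-6 PET, change and response are measured together. Section 9.2 says only that response follows standard of care, so this is conditional. Only the baseline values are certain to come before response.
- **Missing pairs.** Section 9.4.5 asks for the same lesion to be re-biopsied only where feasible. A completely regressed lesion, which 11.2 counts as responding, would presumably yield no week-6 tissue, yet its baseline score would exist.

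**Working it through.** **Text check.** The plan has no figure to reproduce here.

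| Place | What is related to response |
|---|---|
| Summary | PD-L1 expression, time point not given |
| 3.2, 9.2 | Baseline-to-week-6 difference |
| 11 (opening) | Generic non-parametric tests, tied to no comparison |
| 11.1 | Nothing (SUV against IHC only) |
| 11.2 | SUV increase; IHC difference |

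No entry names baseline level against response.

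**Can change stand in for baseline?** Everything in this step is assumed: normal uptake, equal variances, and baseline/week-6 correlation r of 0.2, 0.5 or 0.8. Let d be the responders' standardised excess uptake at baseline and g·d their excess at week 6.

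- d = √2·z(AUC). For AUC 0.80, d = √2 × 0.842 = 1.190. For AUC 0.65, d = 0.545.
- Change has mean shift (g − 1)d and SD √(2(1 − r)), so AUC for change = Φ[(g − 1)d / (2√(1 − r))].
- Example with r = 0.5, g = 0.5: Φ(−0.595/1.414) = Φ(−0.421) = 0.337.

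| Baseline AUC | Excess at week 6 | r = 0.2 | r = 0.5 | r = 0.8 |
|---|---|---|---|---|
| 0.80 | shrinks by factor r | 0.30 | 0.34 | 0.40 |
| 0.80 | constant (g = 1) | 0.50 | 0.50 | 0.50 |
| 0.80 | grows 1.5-fold | 0.63 | 0.66 | 0.75 |
| 0.65 | shrinks by factor r | 0.40 | 0.42 | 0.45 |
| 0.65 | constant (g = 1) | 0.50 | 0.50 | 0.50 |
| 0.65 | grows 1.5-fold | 0.56 | 0.58 | 0.62 |

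Change equals baseline in AUC when g = 1 + √(2(1 − r)), that is 2.26, 2.00 and 1.63 for the three correlations, whatever the baseline AUC. Above that, change does better.

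A second check uses the correlation between baseline and change, (kr − 1)/√(1 + k² − 2kr), where k is the week-6/baseline SD ratio. For r from 0.3 to 0.9 and k from 0.6 to 1.4 it runs from −0.87 to +0.39. Sign and size both depend on values the documents do not give.

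**Scale from section 2.2.** For a two-level marker, AUC = [P(high | response) + P(low | no response)]/2. The share of high expressers is assumed.

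- 17% against 30%, 70% high: (0.210/0.261 + 0.249/0.739)/2 = 0.57.
- 8% against 45%, 30% high: (0.135/0.191 + 0.644/0.809)/2 = 0.75.

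These are patient-level objective response rates in NSCLC. Section 11.2 works per lesion and counts stable disease as responding, so they give only a rough scale.

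**Precision of a baseline display at AUC 0.80 (95% half-widths).**

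- Baseline IHC, one lesion per patient, 10 patients (Hanley-McNeil): 0.29 for 5 responders and 5 non-responders, 0.34 for 3 and 7.
- Lesion SUV, by simulation with half the lesions responding, 3 to 5 lesions per patient and intraclass correlation 0.3 to 0.7 (the same for uptake and latent response): 0.14 to 0.22 with 10 patients, 0.11 to 0.17 with 15.
- Treating lesions as independent in 10 patients would give 0.12 (25:25) to 0.16 (15:15), which is too narrow.

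**The case against.** The strongest reply is that the operative sections agree with each other. Sections 3.2 and 9.2 define the response question as change against response, and 11.2 analyses exactly that. The Summary objective can be read as shorthand for 3.2, and section 2.3 speaks of serial scanning and an early biomarker, which suits on-treatment change. On this reading the fault is one word, and 11.2 could simply be relabelled. This supports keeping the change analyses. It does not account for 11.2's own stated aim, which is prediction, or for the patient-selection use named in 2.3.

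A second reply is size and purpose. Section 11 calls the study exploratory, and 11.2 concedes that the population is too small. No data are lost, no decision depends on the result, and the plot could be made later. All of this stands and limits the weight of the point. A later plot would not be prespecified, however, and a study meant to supply base statistics for further research is a natural place for such a display. The display would not settle the baseline question either.

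Third, the AUC figures rest on assumptions, and under some of them change outperforms baseline. That is correct. They show only that the two can diverge in size and direction. The 15-patient precision also assumes usable lesion response in phase one, whereas 9.4.3 specifies a diagnostic CT only for phase two.

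**Conclusion.** The concern holds. Section 11.2 states a prediction aim and supplies only on-treatment change analyses; no analysis in section 11 relates baseline SUV or baseline IHC to response. That conclusion rests on the text alone.

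The size of the gap between change and baseline cannot be fixed from the documents. In the illustrative model a null or reversed result for change is compatible with a clearly predictive baseline level, so the change result cannot answer the baseline question in either direction.

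The omission is worth correcting but does not threaten the study. Scan timing in phase one and the PET-IHC validation in phase two are untouched.

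**What to change.** Add to section 11.2:

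> Baseline SUVmax and SUVmean of each lesion scored for response, and the baseline PD-L1 IHC score of the biopsied lesion (phase two), will be plotted and tabulated by response, with patients identified. This is descriptive only.

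Keep SUV change and IHC change against response, labelled as a separate pharmacodynamic or early-marker analysis. Matching wording in 3.2 and 9.2 would be tidy, but the fix works without it.

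The cost is one sentence, one plot and one table from data already collected, with no added patients, scans or biopsies. The downside is one more exploratory comparison in at most 15 patients with clustered lesions, so it should carry no significance claim.
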